5.13 Pharmacodynamic Biomarkers

Whole blood and urine PD samples collected at the Baseline and Week 24 visits and plasma PD samples collected at the Baseline, Week 4, Week 8, and Week 24 visits will be analyzed according to a separate PD analysis plan. The PD analysis plan will be finalized prior to database lock.

5.14 Pharmacokinetics of Riluzole

Plasma samples collected at the Baseline, Week 4, and Week 8 visits from the first forty (40) RGC participants taking riluzole who reach the Week 8 visit plus plasma samples collected at the Baseline Visit from an additional ten (10) RGC participants not taking riluzole will be analyzed to quantify riluzole concentration by high-performance liquid chromatography mass spectroscopy (LC/MS/MS) [Covance, Method ID: M10125, Study Number 8454-985].

5.15 Clinical Safety Laboratory Tests

Clinical safety labs include hematology, blood chemistry panel, liver function tests, thyroid function, urinalysis, and pregnancy testing in women of childbearing potential as specified in Section 9.1.2 Clinical Safety Laboratory Tests of the Master Protocol:

- Hematology: hematocrit, hemoglobin, platelet count, red blood cell (RBC) count, mean corpuscular volume, mean corpuscular hemoglobin, mean corpuscular hemoglobin concentration, RBC distribution width (RDW), RBC morphology, white blood cell (WBC) count, and counts and percentages of basophils, eosinophils, lymphocytes, monocytes, and neutrophils;
- Blood chemistry panel: bicarbonate, chloride, potassium, sodium, calcium, magnesium, phosphate, blood urea nitrogen, creatinine, estimated glomerular filtration rate (eGFR) calculated using the Modification of Diet in Renal Disease (MDRD) four-variable equation, creatinine clearance calculated using the Cockcroft-Gault equation, and glucose;
- Liver function tests: alanine aminotransferase (ALT [SGPT]), aspartate aminotransferase (AST [SGOT]), alkaline phosphatase (ALP), albumin, total protein, total bilirubin (TBL);
- Thyroid function tests: thyroid-stimulating hormone (TSH);
- Urinalysis: clarity, color, specific gravity, pH, microalbumin, protein, glucose, ketones, bilirubin, urobilinogen, nitrite, leukocyte esterase, and blood; and
- Pregnancy: qualitative and quantitative serum human chorionic gonadotropin (hCG).

Clinical safety labs will also include derived measures of potential drug-induced liver injury (DILI), including those that potentially meet the Hy's law criteria, as distinct safety lab outcomes.

Three potential DILI criteria will be defined:

- ALT or AST >3x ULN with TBL >1.5x ULN
- AST or ALT >3x ULN with TBL >2x ULN
- AST or ALT >3x ULN with TBL >2x ULN and ALP <2x ULN (potential Hy's Law cases)

where ULN is upper level of normal and all levels are measured on the same day.

6. Statistical Methodology

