5.11 Regimen-Specific Lab Alerts

Site Investigators and the Medical Monitor will receive an alert from the Central Lab for certain lab changes. (See below.) These alerts are informative only, and they do not mean a participant must reduce drug dosage or discontinue study drug. These alerts indicate that the Site Investigator and Medical Monitor should follow up with additional testing and management as clinically indicated. Discontinuation of any participant on the basis of abnormal laboratory findings will be at the discretion of the Site Investigator.

Chemistry Panel Test Name	Outlier Criteria Warranting Further Investigation
ALT and AST	>3x ULN
Creatinine	>1.5 x Baseline
Hematology Panel Test Name	Outlier Criteria Warranting Further Investigation
Platelet count	<75,000/mm ³

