2.9 RGC Schedule of Activities (SoA)

Activity	MP	RGC	Base-	Week	Week	Week	Week	Week	Week	Week	Final
	Scrn ¹	Scrn ²	line	2	4 ³	8 ³	12	16	20	24 ³	Call ⁴
	Cln	Cln	Cln	Phn	Cln ⁵	Cln ⁵	Phn	Cln ⁵	Phn	Cln	Phn
	-42d	-41d	Day	Day	Day	Day	Day	Day	Day	Day	28d ±3
	to -1d	to 0d	0	14±3	28±7	56±7	84±3	112±7	140±3	168±7	ALD
Written Informed Consent ⁶	X	X									
Inclusion/Exclusion Review ⁷	X	X									
ALS & Medical History	X										
Demographics	X										
Physical Examination	X										
Neurological Exam	X										
Vital Signs ⁸	X		X		X	X		X		X	
Slow Vital Capacity	X ⁹		X			C		C		X	
Home Spirometry	X ⁹		X			X		X		X	
Muscle Strength Assessment			X			C		C		X	
ALSFRS-R	X		X		X	X	X	X	X	X	
ALSAQ-40			X							X	
CNS-BFS			X			X		X		X	
12-Lead ECG	X									X	
Clinical Safety Labs ¹⁰	X		X		X	X		X		X	
CNM-Au8 PK Samples ¹¹			X		C	C				X	
CNM-Au8 PD Samples ¹¹			X		C	C				X	
Biomarker Blood Collection ¹¹			X			C		C		X	
Biomarker Urine Collection ¹¹			X			C		C		X	
DNA Collection ¹² (optional)			X								
CSF Collection (optional)			X					C ¹³			
Concomitant Medication Review	X	X	X	X	X	X	X	X	X	X	
Adverse Event Review ¹⁴	X	X	X	X	X	X	X	X	X	X	X
Suicidality C-SSRS			X		X	X		X		X	
Install Smartphone Apps ¹⁵			X								
Smartphone Voice Recording ¹⁶			X		X	X		X		X	
Uninstall Smartphone App										X	
Regimen Assignment	X										

Activity	MP Scrn ¹	RGC Scrn ²	Base-line	Week 2	Week 4 ³	Week 8 ³	Week 12	Week 16	Week 20	Week 24 ³	Final Call ⁴
	Cln	Cln	Cln	Phn	Cln ⁵	Cln ⁵	Phn	Cln ⁵	Phn	Cln	Phn
	-42d to -1d	-41d to 0d	Day 0	Day 14±3	Day 28±7	Day 56±7	Day 84±3	Day 112±7	Day 140±3	Day 168±7	28d ±3 ALD
Randomization within RGC			X								
Administer/Dispense Study Drug			X ¹⁷			X		X			
Drug Accountability/Compliance				X ¹⁸	X	X	X ¹⁸	X	X ¹⁸	X	
Exit Questionnaire										X	
Vital Status										X ¹⁹	

Abbreviations: ALD = after last dose, ALS = amyotrophic lateral sclerosis, ALSAQ-40 = ALS Assessment Questionnaire, ALSFRS-R = ALS Functional Rating Scale Revised, BP = blood pressure, C = completed only if the visit is conducted in-clinic, CBC = complete blood count, Cln = Clinic visit, CNS-BFS = Center for Neurologic Study Bulbar Function Scale, CSF = cerebrospinal fluid, C-SSRS = Columbia-Suicide Severity Rating Scale, d = day, DNA = deoxyribonucleic acid, ECG = electrocardiogram, LFTs = liver function tests, MP = Master Protocol, PD = pharmacodynamic, Phn = Phone visit, RGC = the CNM-Au8 regimen, Scrn = Screening Visit.

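### The SAP's same-day rule for potential DILI and Hy's Law cases has no pairing window, so a case whose bilirubin rises after transaminases have fallen to 3x ULN or below is not counted

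*SAP*

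**What the plan says.** SAP 5.15 (Clinical Safety Laboratory Tests) makes the derived liver-injury measures safety laboratory outcomes in their own right. The first criterion is "ALT or AST >3x ULN with TBL >1.5x ULN". The second raises the bilirubin multiple to 2x ULN. The third, labelled potential Hy's Law, adds ALP below 2x ULN. The timing rule for all three is "where ULN is upper level of normal and all levels are measured on the same day". No look-back or look-forward window is given. The section does not say whether unscheduled or repeat results enter the derivation.

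Protocol 5.11 (Regimen-Specific Lab Alerts) sends a central laboratory alert to the site investigator and the medical monitor when ALT or AST exceeds 3x ULN. On what follows it says: "These alerts indicate that the Site Investigator and Medical Monitor should follow up with additional testing and management as clinically indicated". It fixes no panel, timing or laboratory for that testing. Bilirubin and ALP are not in its table.

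SAP 6.6.2 (Safety Labs) tabulates CTCAE grades (visit by visit and as the post-baseline maximum) and shift tables for ALT and AST above 3x ULN. It takes its other rules from the M-SAP, which is not among the supplied documents. SAP section 1 ranks the R-SAP above the M-SAP on analysis matters of this kind.

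**The concern.** A same-day rule fits when all abnormalities peak together. It fits less well if bilirubin rises after the transaminases have begun to fall. Scheduled post-baseline safety labs fall only at Weeks 4, 8, 16 and 24, so what happens after an alert is seen mainly on unscheduled retests. The rule cannot join an ALT value from the alert day to a bilirubin value from a later day.

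At stake is the count of potential Hy's Law cases. Protocol 5.10.1.1 reports human dosing of up to 21 consecutive days, and Protocol 5.10.1.2 expects slow elimination with accumulation in blood and tissue. With so little prior exposure, a reported count of zero should mean that no joint abnormality was seen, not that its two halves fell on different days.

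**Working it through.** The plan gives no figure to reproduce here. The check applies the rule as written to hypothetical laboratory sequences.

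**Inputs from the documents.** Criteria and timing rule: SAP 5.15. Alert threshold: Protocol 5.11. Lab days 0, 28, 56, 112 and 168: SAP 2.9. Gaps: 28 − 0 = 28, 56 − 28 = 28, 112 − 56 = 56, 168 − 112 = 56 days. Planned active participants: 120 (Protocol, Number of Planned Participants and Treatment Groups).

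**Assumed inputs.** All laboratory values, the ALT half-lives and the window lengths below. The documents give none of them.

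**Step 1: two sequences (values in multiples of ULN).**

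| Case | Day | ALT | TBL | ALP |
|---|---|---|---|---|
| A | 56 | 6 | 1.2 | 1.1 |
| A | 63 | 4.5 | 2.4 | 1.2 |
| B | 56 | 6 | 1.2 | 1.1 |
| B | 66 | 2.6 | 2.4 | 1.2 |

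- Case A, same-day rule: on Day 63, 4.5 > 3, 2.4 > 2 and 1.2 < 2, so all three criteria are met. A window adds nothing. If only the Day 56 result were in the analysis data, the case would be lost, because 1.2 is not above 1.5.
- Case B, same-day rule: on Day 56 bilirubin fails (1.2 is not above 1.5). On Day 66 ALT fails (2.6 is not above 3). No criterion is met on either day.
- Case B, paired: ALT 6 > 3 and ALP 1.1 < 2 on Day 56, TBL 2.4 > 2 on Day 66. All three criteria are met. The lag is 66 − 56 = 10 days, so a 7-day window misses it and a 14- or 30-day window finds it.

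**Step 2: how long a lag the same-day rule tolerates.** Suppose ALT is P x ULN at the alert and decays with half-life h days. It stays above 3x ULN for L = h × log2(P/3) days, and a bilirubin rise lagging by less than L can still be caught on one day.

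| P | h = 2 | h = 4 | h = 7 | h = 14 |
|---|---|---|---|---|
| 5 | 1.5 | 2.9 | 5.2 | 10.3 |
| 10 | 3.5 | 6.9 | 12.2 | 24.3 |
| 20 | 5.5 | 10.9 | 19.2 | 38.3 |

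The tolerated lag runs from under two days to more than five weeks. The rule is weakest for moderate, quickly falling ALT.

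**Step 3: is the joint case recovered elsewhere?** The SAP 6.6.2 tables work analyte by analyte. They would show the Case B participant with ALT above 3x ULN, and separately with a graded bilirubin value if the retest is in the data. Nothing joins the two.

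**Step 4: what one case does to the count.** With 0 of 120, the one-sided 95% exact upper bound is 1 − 0.05^(1/120) = 2.5%. With 1 of 120, it solves (1 − p)^120 + 120p(1 − p)^119 = 0.05, giving 3.9%.

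**The case against.** The strongest reply is that the rule is tied to a day, not to a scheduled visit or to the alert day. ALT, AST, ALP and bilirubin all sit in the one liver panel listed in SAP 5.15, so a full-panel retest can qualify on its own date. That stands, and Case A shows it. A reader might infer that the plan throws away the tests its own alert generates, or that any case emerging on follow-up is missed. The documents do not support this: neither SAP 5.15 nor SAP 6.6.2 excludes retests.

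It can also be said that patients are protected by Protocol 5.11, not by an analysis variable. That stands too. The alert fires on ALT or AST whatever the bilirubin, and the participant remains visible in the transaminase tables. Only the joint flag is lost.

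A reader might go further and see a conflict between the alert list, which omits bilirubin, and the SAP criteria, which all need it. There is none. Every SAP criterion requires the transaminase condition that already triggers the alert, and the two lists serve different purposes.

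The M-SAP may say how unscheduled results are handled, so silence in the supplied documents is not proof of a gap on that question. It would not cure the timing rule, because the R-SAP prevails where the two differ.

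Finally, pairing relies on retests, and retesting may differ between regimens. The safety sets STF and STN include shared placebo participants (SAP 6.1), while the Protocol 5.11 alerts are specific to this regimen. This is a fair caution about comparing counts. It is not a reason to leave the cases uncounted.

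**Conclusion.** The concern holds in a limited form. The criteria are same-day only, and no other analysis in the supplied documents joins transaminases with bilirubin. A participant is counted negative in two situations: bilirubin crosses after ALT and AST have reached 3x ULN or below, or the retest does not measure every component on one day. A third loss would arise if retest results are left out of the analysis data, which the supplied documents do not settle.

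The number affected cannot be derived from the documents and is probably small. That bilirubin may lag the transaminases is an assumption, as are the laboratory values and half-lives above. One case in 120 moves the upper bound only from 2.5% to 3.9%. The greater value lies in identifying that participant as a potential Hy's Law case. The consequence is for safety case counting and reporting, not for clinical follow-up. The documents do not support replacing the same-day rule or changing the alert list. The addition below is cheap and should be made.

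**What to change.** In SAP 5.15:

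1. Keep the same-day count as it stands.
2. Add a second derivation that pairs ALT or AST above 3x ULN with bilirubin above the stated multiple on the same day or within a prespecified window afterwards. Take ALP on the day of the qualifying ALT or AST value. Thirty days is one example; the sponsor should choose and justify the length.
3. State that unscheduled and repeat results in the database are included, under the same rule for active and shared placebo participants.

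A 30-day window can link nominal Weeks 4 and 8 (28 days apart) but not Weeks 8 and 16 or Weeks 16 and 24 (56 days each). In the later intervals it therefore works only through unscheduled results, which makes item 3 essential.

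The cost is SAP wording and one extra derived variable. Because same-day pairs remain eligible, the windowed count can only add flags. Some will be unrelated bilirubin rises that need medical review. Retesting may be unequal across regimens, and this should be noted wherever active and shared placebo counts are compared. Protocol 5.11 needs no change.

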6.1 Analysis Sets

The ITT analysis set is henceforth referred to as the Full Analysis Set (FAS) and defined as follows:

- Full Analysis Set (FAS): Participants who were randomized within RGC plus placebo participants from specified regimens, classified according to their randomized treatment assignment. Observations made after premature permanent discontinuation of study drug are included in this sample, should such participants remain on study. Observations completed after regimen data lock are excluded. Participants determined to not meet ALS diagnostic criteria are excluded.

The definition of the STF analysis set is revised as follows:

- Safety Full (STF) Set: Participants who initiated treatment within RGC plus placebo participants from specified regimens who are not known to be ineligible for RGC and who initiated treatment in their respective regimen, classified according to the treatment they

actually received. Observations made after premature permanent discontinuation of study drug are included in this sample, should such participants remain on study. Observations completed after regimen data lock are excluded.

An analysis set restricting shared placebo participants to those regimens in which study drug is administered by the same route as RGC is defined as follows:

- Efficacy Common Mode of Administration (ECM) Set: The subset of participants in the FAS analysis set who are in regimens in which study drug is administered by the same route as RGC (oral administration).

The definitions of the ECC, ERO, STN, and SRO analysis sets are the same as described in the M-SAP with reference to the ITT analysis set now referencing the FAS analysis set. The following analysis set is specific to RGC:

- Efficacy Per-protocol (EPP) Set: The subset of participants in the FAS analysis set who initiated study treatment and who were not involved in protocol deviations that affected the scientific integrity of the trial as documented prior to data lock, classified according to the treatment they actually received. Inclusion or exclusion from the EPP analysis set of any participant for whom treatment assignment was unblinded prior to data lock will be governed by the prespecified criteria above. If a participant's data is truncated for inclusion in the EPP analysis set due to non-adherence to protocol-specified dosing, clinical events observed up to 28 days after the censoring event will be included in the EPP analysis set. For all other events leading to truncation of a participant's data, no events beyond that date will be included. Data from placebo participants shared from other regimens will not be truncated due to non-adherence to protocol-specified dosing.

Applicable analysis sets (FAS, ECM, EPP, STF, and STN) will include shared placebo participants from regimens A, B, and D. Data from shared placebo participants will include visits and events that occurred on or before the date of the final placebo-controlled period follow-up of an RGA, RGB, or RGC participant. As only concurrently enrolling regimens are contributing to efficacy analyses, the FAS and ECC analysis sets are synonymous and only the FAS analysis set will be referenced. As regimen A is administered by subcutaneous injection and regimens B and D are administered orally, only regimens B and D will contribute shared placebo participants for the ECM and STN analysis sets.

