3.0 (continued)	22 Jul 2022 (continued)	
Revision of Section 5.7 ALSAQ-40 to specify calculation of domain scores and to revise calculation of overall ALSAQ-40 SI.
 
Revision of Section 5.8 CNS-BFS to specify that the total score is referenced.
 
Revision of Section 5.9 Survival to specify that time at risk begins at each participant's Baseline Visit and to specify that the date of PAV initiation, where applicable, will be imputed as the fifteenth day of a month if not specified more precisely.
 
Revision of Section 6.1 Analysis Sets to add the Efficacy Common Mode of Administration (ECM) analysis set, to remove the restriction on protocol deviations that could be considered for exclusion from the Efficacy Per-protocol (EPP) analysis set must be classified as major protocol deviations, to specify the time point at which data is excluded from the EPP analysis set in the case of time-dependent exclusions, and to specify that data from placebo participants from other regimens would not be excluded from the EPP analysis set due to non-adherence to protocol-specified dosing.
 
Revision of Section 6.2 Baseline Characterization to include ALSAQ-40 domain scores and SI, urinary p75[ECD], and vital capacity predicted from quantitative voice characteristics.
 
Revision of Section 6.5.2 CAFS to clarify that the primary CAFS analysis is specified in the ALS Master Protocol Recommended Statistical Analysis, Design and Simulation Report and is an adjusted analysis, to provide code for an adjusted analysis, and to add three additional sets of CAFS analyses, one set that adjusts rank scores in linear models for time from ALS symptom onset, delta-FRS, baseline use of riluzole, and baseline use of edaravone, one set that adjusts for the same set of covariates plus baseline serum NfL level, and one that makes no adjustment.
 
Revision of Section 6.5.3 Repeated-measures Model to add a fixed term for treatment group (removing the shared-baseline assumption at the recommendation of the FDA) and to specify a separate supportive analysis that includes fixed terms for centered baseline serum NfL level, and centered baseline serum NfL level \times visit interaction for analysis of clinical endpoints.
 
Revision of Section 6.5.4 Survival to include ECM as an additional analysis set, to include baseline age as an additional covariate in all adjusted models, and to specify an additional adjusted analysis that includes baseline serum NfL level.

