6.3 Primary Efficacy Analysis and Supportive Analyses

The primary analysis for RGC is a Bayesian shared-parameter, repeated-measures model of ALSFRS-R that accounts for loss of follow-up due to mortality. Details of the model, including documentation of operating characteristics under a range of scenarios, are provided in the "ALS Master Protocol Recommended Statistical Analysis, Design and Simulation Report" (Appendix 1 to the Master Protocol). The Bayesian shared-parameter, repeated-measures model will be

applied to the FAS analysis set as the primary analysis, to the ECM and ERO analysis sets as sensitivity analyses, and to the EPP analysis set as a supportive analysis.

The estimand of the primary analysis is the relative rate of disease progression (the "disease rate ratio" or DRR) of the two active treatment groups relative to placebo in the FAS population under an assumption that active treatment slows mean time to death or death equivalent by the same proportion as treatment slows the mean rate of functional progression as measured by change in ALSFRS-R total score over time. The estimand is defined by the following attributes:

- Treatment: CNM-Au8 administered orally at dosages of 30 mg/d and 60 mg/d vs. placebo.
- Population: FAS population as defined in Section 6.1.
- Variables: time to death or death equivalent and rate of change in ALSFRS-R total score from baseline to the Week 24 Visit.
- Intercurrent event 1: treatment discontinuation due to death: no ALSFRS-R data from participants who reach the death or death equivalent endpoint are included in the analysis; instead, death or death equivalent are handled by a mortality component within the model, composite variable strategy approach.
- Intercurrent event 2: treatment discontinuation not due to death: handled via treatment policy approach, all data will be used including data collected during the placebo-controlled period after treatment discontinuation regardless of concomitant medication, for those participants who have not been censored due to mortality. Missing data post-treatment will not be imputed, handled via missing at random assumption.
- Population-level summary: mean ratio of hazard or progression rate of active treatment relative to placebo.

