6.7 Other Analyses

6.7.1 Participant Disposition

All participants consented to the Master Protocol between the time of the first and last consent of a participant assigned to a regimen included in the FAS analysis set will be summarized as a single set for the following events: consented to the Master Protocol, failed screening for the Master Protocol, other reasons not assigned to a regimen (including timing out of the screening window, death, withdrawal of consent, early termination, and administrative termination), and assigned to a regimen. Reasons for Master Protocol screen failure will be summarized.

All participants in the above sample assigned to a regimen will be summarized as two sets (final screening for RGC vs. final screening for a non-RGC regimen) for the following events: consented to a regimen, failed screening for a regimen, other reasons not randomized within a regimen (including timing out of the screening window, death, withdrawal of consent, early termination, and administrative termination), and randomized within a regimen. If a given individual is screened multiple times prior to randomization within a regimen, then the final screening experience of that individual will be summarized. Reasons for RGC screen failure will be summarized separately for all participants screened for RGC whether that was their final screening experience or not.

All participants in the FAS analysis set will be summarized as two sets (randomization to active study drug vs. randomization to placebo) for the following events: initiated regimen-specific study drug, prematurely terminated study participation due to death, withdrawal of consent, early termination, loss to follow-up, or administrative termination, completed 24-week follow up, and completed a safety follow-up visit vs. continued into the OLE. Reasons for withdrawal of consent or early termination after randomization will be summarized.

Any randomized participants excluded from the FAS and EPP analysis sets or included in the FAS analysis set but not contributing to the primary analysis will be identified in a listing together with the reason for their exclusion.

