6.7.2 Study Drug Compliance and Tolerance

Summaries of study drug compliance and tolerance are the same as specified in the M-SAP with the clarification that summaries will be reported for the ERO and SRO analysis sets and that date of permanent discontinuation of study drug is the date of last use of double-blind study drug among all participants in a given analysis set.

The number of days of exposure to study drug will be calculated in three ways:

- as the number of days from dose initiation to the final safety assessment during the placebo-controlled period, inclusive,
- as the number of days from dose initiation to drug withdrawal, inclusive, less any interval during which use of study drug was interrupted (individual missed doses will not be subtracted unless noted in the dosage management log), and
- as the number of days from dose initiation to the earlier of final contact during the placebo-controlled period or 28 days after last dose of study drug, inclusive.

The proportion of participants who interrupted study drug or reduced study drug dosage and the time to first study drug interruption or dosage reduction will be summarized. The number of days of exposure to a reduced dosage of study drug will be summarized.

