6.7.6 Protocol Deviations

The number of major and minor protocol deviations will be summarized by type of deviation and treatment group in all analysis sets. Listings of all protocol deviations will be produced.

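### The per-protocol (EPP) set can truncate any Regimen C participant for non-adherence but never a placebo participant shared from Regimens A, B or D, so supportive EPP results can shift without a drug effect

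*SAP*

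**What the plan says.** SAP 6.1 builds the EPP set from FAS participants who started treatment and had no deviation damaging the trial's scientific integrity. When data are truncated for non-adherence to dosing, "clinical events observed up to 28 days after the censoring event will be included in the EPP analysis set". For any other reason for truncation, nothing after that date counts. The exemption follows: "Data from placebo participants shared from other regimens will not be truncated due to non-adherence to protocol-specified dosing". It covers this one reason only; the other EPP exclusions still reach shared controls. The set does contain them: "Applicable analysis sets (FAS, ECM, EPP, STF, and STN) will include shared placebo participants from regimens A, B, and D".

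The SAP revision history lists the exemption under version 3.0 ("data from placebo participants from other regimens would not be excluded from the EPP analysis set due to non-adherence"), so it is deliberate. The documents supplied give no reason for it.

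The EPP set has three named uses. SAP 6.3 applies the Bayesian ALSFRS-R and mortality model "to the EPP analysis set as a supportive analysis". SAP 6.5.4 uses the set for survival to the end of the placebo-controlled period, and 6.5.6 for hospitalization and other clinical events.

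Three outputs bear on visibility:
- SAP 6.7.1 lists, with reasons, "Any randomized participants excluded from the FAS and EPP analysis sets".
- SAP 6.7.2 says that compliance "summaries will be reported for the ERO and SRO analysis sets", neither of which is among the sets that 6.1 names as including shared placebo.
- SAP 6.7.6 says: "The number of major and minor protocol deviations will be summarized by type of deviation and treatment group in all analysis sets". It also provides listings of all deviations.

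**The concern.** The rule follows regimen of origin, not treatment arm. All active participants are in Regimen C, so in practice it separates the arms: the whole active group is open to truncation, but only the Regimen C part of the pooled placebo group is. Two kinds of placebo participant inside one comparator are also handled differently.

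Suppose participants who stop taking drug then die or decline at a different rate. Most of that later experience is removed from the active arm and kept for the exempt controls. The comparison can then differ from no effect when the drug does nothing. What is at stake is the value of EPP as support: it should show whether the FAS result holds among adherent participants, and a handling difference between arms blurs that. No success criterion depends on it.

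**Working it through.** **1. Plan figures.** The documents state no sample size or precision for EPP, so there is nothing of that kind to reproduce. The allocation checks: 160 in ratio 3:3:2 (SAP 2.6) gives 160 × 6/8 = 120 active and 160 × 2/8 = 40 placebo, as in the protocol summary.

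**2. Exempt share of controls.** This is S/(S + 40), where S is the number of shared placebo participants. S is not in the documents. With S = 60: 60/100 = 60%. With S = 120: 120/160 = 75%. In the active arm it is 0/120.

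**3. Survival with no drug effect.** From the documents: 120 active, 40 own placebo, 168 days, and the 28-day event allowance. Assumed: S = 60 or 120; 24-week mortality m = 4, 8 or 12%; non-adherence by week 24 p = 7 to 30%; death hazard λ while adherent and kλ afterwards, with k = 0.5, 1, 2 or 4.

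- Non-adherence hazard per day: μ = −ln(1 − p)/168.
- λ is set so that untruncated 24-week mortality equals m.
- Adherent and at risk at day t: a(t) = exp[−(λ + μ)t].
- Non-adherent and at risk: b(t) = ∫ μ exp[−(λ + μ)s] exp[−kλ(t − s)] ds, from s = max(0, t − 28) to t if truncated, or from 0 to t if exempt.
- Death rate: e(t) = λ[a(t) + k b(t)], with a, b and e scaled by group size. The number at risk is Y = a + b.
- Hazard ratio (Mantel–Haenszel): ∫ e_A Y_P/(Y_A + Y_P) dt ÷ ∫ e_P Y_A/(Y_A + Y_P) dt.
- Var(log HR) = 1 ÷ ∫ (e_A + e_P) Y_A Y_P/(Y_A + Y_P)² dt.

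*One case in full* (m = 8%, p = 20%, k = 4, S = 120). Here 168μ = −ln 0.8 = 0.223 and 168λ = 0.0644.
- Active: 7.63 expected deaths over 18,112 participant-days, or 0.421 per 1,000.
- Pooled controls: 12.14 over 25,437, or 0.477 per 1,000.
- HR = 0.884, SE(log HR) = 0.457, shift = ln 0.884/0.457 = −0.123/0.457 = −0.27 SE.
- Regimen C controls alone: 2.54 deaths over 6,037 days, again 0.421 per 1,000, so HR = 1.00, with SE 0.724.

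*All cases, equal non-adherence in every group:*

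| Hazard after non-adherence | HR under SAP rule | HR with one rule, or Regimen C only |
|---|---|---|
| halves | 1.007–1.042 | 1.000 |
| unchanged | 1.000 | 1.000 |
| doubles | 0.932–0.987 | 1.000 |
| fourfold | 0.835–0.965 | 1.000 |

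Expected events run from 7 to 33 and SE(log HR) from 0.35 to 0.76. The largest shift (p = 30%, k = 4, m = 12%, S = 120) is ln 0.846/0.383 = −0.167/0.383 = −0.44 SE. With a doubled hazard the largest is 0.18 SE.

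*Unequal non-adherence (fourfold hazard, 8% placebo mortality, same hazards in both arms within each adherence state):*

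| Active vs placebo non-adherence | SAP rule | One rule, or Regimen C only |
|---|---|---|
| 30% vs 10% | 1.036–1.048 | 1.103 |
| 20% vs 10% | 0.984–0.996 | 1.049 |
| 10% vs 30% | 0.758–0.781 | 0.906 |

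In the first two rows the SAP rule lies nearer 1.00; in the third it lies further away.

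**4. Function.** No size can be given, because the Bayesian model is not in the documents. Bias is expected only if stopping depends on progression not yet observed, or if decline changes after stopping. It is not expected if stopping follows already observed scores and the missing-at-random assumption holds.

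**The case against.** The best defence is that this is a considered choice in a supportive analysis. Shared controls would have to be judged by other regimens' dosing rules; Regimen A, for instance, is subcutaneous. Whether those records are usable cannot be told from these documents. It can also be argued that missed placebo doses do not change drug exposure. That argument would exempt Regimen C's own placebo participants too, and they are not exempt.

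Several points against the concern stand:
- Each of the three EPP uses is also run in FAS, ECM and ERO, where the exemption plays no part, so a divergent EPP result would be visible. None of those sets is per-protocol, however, and no EPP analysis limited to Regimen C is named.
- The rates are unanchored. SAP 6.1 sets no non-adherence threshold. Protocol 5.7 gives 80–120% of planned dose for the per-protocol set, but no expected frequency of departures.
- A reader might infer that shared-control non-adherence stays hidden. The documents do not support that. FAS placebo contains shared controls and ERO does not, so subtracting the 6.7.6 summaries, or reading the listings, may recover much of it where it is logged as a deviation. What remains missing is narrower: no planned output counts participants truncated for non-adherence by arm and regimen.
- A reader might infer that the exemption should simply be replaced by one rule for everyone. The unequal-adherence results show that this is a trade-off.
- Protocol 5.7 might be read as contradicting the exemption. SAP Section 1 makes the regimen SAP authoritative on shared placebos, so it does not.

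**Conclusion.** The asymmetry is explicit and can move supportive EPP results with no drug effect, but only if non-adherence is related to prognosis. Under the assumed rates, with equal non-adherence, the null survival hazard ratio lies between 0.84 and 1.04, at most 0.44 SE from no effect. The sign is not determined, and the size for function cannot be derived. It would go too far to say that the rule favours the drug, or that it affects the trial's conclusions: SAP 6.3 and 6.5.1 place primary and hierarchical inference on the FAS, and the ECM and ERO runs are also untouched. This is an optional improvement, held with medium confidence because every rate and the number of shared controls are assumptions.

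**What to change.** Keep the EPP rule as written. In SAP 6.1, 6.3, 6.5.4 and 6.5.6, add an EPP analysis restricted to Regimen C participants, with the same truncation and the same 28-day event allowance in both arms. Report the number truncated for non-adherence by arm and regimen, and state the reason for the exemption in a sentence. If the other regimens' dosing records prove usable, an EPP version applying the same rule to shared placebo, judged against each regimen's own dosing, may be shown alongside but not as a replacement.

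The cost is a few sentences, one count table and some programming before data lock, using data Regimen C already holds. The drawback is precision: with about 40 controls, SE(log HR) in the worked case rises from 0.457 to 0.724. The added run removes the bias caused by the exemption. It does not remove bias from different non-adherence rates between arms, which any per-protocol analysis can carry.
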